Chief Investigator	[name] Queen Alexandra Hospital [name] [contact] [name]
Lead Researcher	[name] [name] Queen Alexandra Hospital [name] [contact] [name]
Sponsor	[name] Research and Development Department Queen Alexandra Hospital [name] [contact] [name]
Funder(s)	National School of Healthcare Science

**Portsmouth Hospitals
University
NHS Trust**

BIO-CHECKPOINT

	[name] [name] [contact]
--	---

BIO-CHECKPOINT

STUDY SUMMARY

Study Title	Characterising biomarkers and clinical algorithms to identify oncology patients on immune checkpoint inhibitors (ICPI) that are at greater risk of developing immune-related adverse events (irAE).
Internal ref. no. (or short title)	BIO-CHECKPOINT
Study Design	Retrospective cohort study
Study Participants	Adult oncology patients at Queen Alexandra hospital, who are prescribed FDA approved ICPI for the first time
Planned Size of Sample (if applicable)	120
Follow up duration (if applicable)	6 months post initiation of ICPI
Planned Study Period	Sample collection = 18 months Data collation and analysis = 6 months Total time = 24 months
Research Question/Aim(s)	Can a clinical algorithm be created to flag high risk Oncology patients that have a greater risk of developing irAE? In addition, can novel biomarkers such as malondialdehyde be incorporated into this algorithm to aid stratification.

FUNDING AND SUPPORT IN KIND

FUNDER(S)	FINANCIAL AND NON-FINANCIAL SUPPORT GIVEN
National School of Healthcare Science	£13,000 per year for 5 years £65,000 total
Royal College of Pathologists	Awarded £1015.60 2 nd of August 2023

BIO-CHECKPOINT

ROLE OF STUDY SPONSOR AND FUNDER

Queen Alexandra Hospital is the sponsor of this research study. However, the responsibility for the design, conduct, data analysis, interpretation, manuscript writing, and dissemination of results falls to the lead researcher [name] [name]. The sponsor will have oversight of the study and ensure that it continues to operate within legal boundaries. The chief investigator and lead researcher are responsible for ensuring that the sponsor is kept informed of changes and updated to the BIO-CHECKPOINT study.

Funder(s) do not control the final decision regarding any of these aspects of the study.

ROLES AND RESPONSIBILITIES OF STUDY MANAGEMENT COMMITTEES/GROUPS & INDIVIDUALS

Study Steering Groups

No study steering groups have been involved in the study coordination and conduct.

Patient and Public Involvement group has been engaged at Portsmouth and research study will be presented to this group. Public presentation will also be given at Manchester May 2024 as part of [name]'s Doctorate in Clinical Biochemistry.

PROTOCOL CONTRIBUTORS

The study design is principally the responsibility of the lead researcher [name] and Chief investigator [name]. The funder the National School of Healthcare Science does not control any aspect of the study. The sponsor the Research and Development office at Portsmouth will review and feedback on the protocol when indicated. The study design will be discussed and review with the Portsmouth Patient involvement group, facilitated by [name].

KEY WORDS:

Check point inhibitors, oncology, cancer, immune related adverse events, blood biomarkers

BIO-CHECKPOINT**STUDY FLOW CHART**

BIO-CHECKPOINT

STUDY PROTOCOL

1.0 LAY SUMMARY –

Immune checkpoint inhibitors (ICPI) are a type of cancer treatment. Unlike traditional chemotherapy and radiation, which damages both the cancer and the healthy tissue, ICPI targets cancer directly by altering the immune system. Cancer cells produce high levels of protein called checkpoint proteins, which bind to white blood cells (which are part of the immune system) and stops them from working. Effectively the cancer is pushing a stop button on the immune system and the body can no longer fight it off. ICPIs block and remove these cancer checkpoint proteins, which allows the immune system to target the cancer again removing this stop button.

ICPI has great success in treating cancer and 10% of oncology NHS patients receive this treatment, although this number is increasing. However, ICPI carries a risk of a type of side effect called immune related adverse events (irAE). irAEs can be life threatening and present with similar symptoms to the patient's cancer. For example, a patient may have kidney cancer and after treatment with ICPI develop kidney failure. It is difficult for the doctor to tell if this is the cancer progressing or a side effect of the treatment. Delays in diagnosing irAE can lead to unnecessary hospitalisation, unnecessary breaks in treatment, lifelong side-effects, and death.

Currently there is not a unified blood test panel for ICPI patients, and the cancer societies have produced little guidance for the doctors to use. At Portsmouth what blood tests you get as an ICPI patient depend on which clinician you see. There is also little research as researchers are focussing on using blood tests to predict ICPI treatment success rather than the chance of a patient developing an irAE.

We intend to conduct a study where we collect leftover blood from routine clinical blood draws on oncology patients being treated with ICPIs for the first time. We will freeze the leftover samples and test them a month later for different routine blood tests as well as malondialdehyde. Malondialdehyde is a blood test that can assess the body's oxidative stress level, a condition where your body lacks antioxidants. Testing for malondialdehyde is not available in the NHS and we would produce a new NHS blood test as part of this study. Once testing is completed the samples will be destroyed as per our normal protocol. At the end of the study, we will correlate the blood test results to the patient's outcome i.e., did they have an irAE or not and assess if there are any differences in their blood test results. From this information we hope to understand which blood tests help to highlight if a patient is at a risk of developing irAE before it occurs. It also aims to develop a new method for measuring malondialdehyde.

BIO-CHECKPOINT

2.0 BACKGROUND

This study aims to identify biomarkers that stratify Oncology patients on immune check point inhibitor (ICPI) that have an increased risk of developing autoimmune toxicity known as immune-related adverse events (irAE).

ICPIs are being increasingly prescribed and 10% of NHS Oncology patients receive treatment from this drug group (1,2). The reported rate of total irAE triggered by ICPI varies but is thought to be between 40-66% (3-5), a third of which are endocrine related (6,7).

Several bodies including the European Society for Medical Oncology, American Society for Clinical Oncology and the National Comprehensive Cancer Network have produced guidance for irAE management, but no unified screening protocol exists to stratify patients at high-risk (8). Currently the literature primarily centres around looking for prognostic biomarkers for treatment success rather than characterising toxicity.

Individual studies review the utilisation of some routine clinical blood tests, i.e., albumin, rheumatoid factor, lactate dehydrogenase, IL-6, etc, to screen and stratify high-risk patients (9,10). However, these tests are used in isolation and no singular clinical algorithm using a variety of routine tests has been developed for initial screening during ICPI therapy. A variety of protocols have been developed for screening endocrine irAE, although these are not consistently adopted, and practice varies.

ICPIs induce an enhanced immunological response to promote anti-tumour activity (11). There are a few forms of ICPI including CTLA-4 antibodies that upregulate T-cell activation pathways to enhance the tumour immune response. There are also antibodies that act as programmed death receptor agonists, which promote cytokine release and T-cell activation. (12)

An array of studies has shown that reactive oxygen species (ROS) are involved in the regulation of T-cell anti-tumour immunity (13–20). ICPI are active therapies that alter T-cell intracellular signalling, which can increase ROS production and proinflammatory cytokine secretion, thus exerting an immunotherapeutic effect (13).

irAE refers to a spectrum of autoimmune toxicities triggered by ICPI. ROS are implicated in the initiation, amplification, pathogenesis of autoimmune diseases (21,22). Are ROS heavily upregulated in irAE due to a dysregulated immune response and could the measurement of an oxidative stress marker act as a marker of toxicity?

Malondialdehyde is generated from ROS driven lipid peroxidation of polyunsaturated fatty acids and is an indirect marker of oxidative stress. Malondialdehyde can be detected within plasma, serum and urine via liquid-chromatography mass-spectrometry (LC-MS/MS). (23–25) Malondialdehyde has been suggested as a future marker of tissue level thyroid dysfunction, the most common irAE is hypothyroidism (26).

BIO-CHECKPOINT

At present, Portsmouth does not have a unified screening process for patients about to commence ICPI and tests requested are clinician dependent. This project seeks to produce a unified clinical algorithm.

3.0 Objectives and Outcomes Measures/Endpoints

3.1 Primary objectives

Can a clinical algorithm be created to flag high risk Oncology patients that have a greater risk of developing irAE? In addition, can novel biomarkers such as malondialdehyde be incorporated into this algorithm to aid stratification.

- P Oncology adult patients on ICPI
- I No intervention – retrospective analysis
- C Comparing blood test results of those who develop irAE to those who don't
- O Are any of the blood tests significantly different in those who develop irAE
- T 6 months follow up post starting treatment, 18 testing period.

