3.2 Secondary objectives

This principal research question will be broken down to the following sub aims:

1. Are there any established biochemistry, haematology and immunology blood tests that produce significantly different results in those who develop irAE when compared to those that don't. Including IL-6 (requires in-house verification). Observational study
2. Can a malondialdehyde LC-MS/MS assay suitable for clinical laboratory use be developed based on a method development by Sobsey *et al.*
3. Is malondialdehyde significantly raised in those who develop irAEs compared to those that do not. An ELISA kit has been located in the event an LC-MS/MS method is not successfully developed.
4. Can a blood test clinical algorithm be developed to stratify patients at high-risk of developing an irAE.

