3.3 Outcome

This project could produce a clinical algorithm and/or blood test panel that successfully highlights patients at a high risk of developing irAE, prior to commencing therapy. This would allow closer monitoring of high-risk patients, leading to earlier diagnosis of irAE. Currently irAE can be tricky to diagnose and have overlapping symptoms with the malignancy and related concomitant treatments (27). Earlier diagnosis would lead to reduced hospitalisation, better outcomes, and reduced

BIO-CHECKPOINT

interruptions to the anti-cancer therapy, which may lead to better malignancy curative rates. There is also a potential to reduce morbidity and mortality risk for this subset of patients, as well as an overall reduction in resource burden.

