4.0 STUDY DESIGN

4.1 SUMMARY OF DESIGN

This is a retrospective cohort study that looks at blood test results correlated to clinical outcomes.

Oncology patients, whom have been prescribed ICPIs for the first time, will be identified via the chemotherapy scheduling system. This study does not require extra blood draws or tubes to be taken. Left over serum and plasma from routine clinical blood draws will be retrieved. This serum and plasma will be aliquoted into tube labelled with a pseudonym reference. The samples will be booked into our laboratory information management system under a pseudonym reference. This system is password protected and only those involved in this research should be accessing these records. Left-over samples will be frozen at -80C and stored for a period of 1 month before being tested in batches. Before testing a list of NHS numbers of the patients that have been recruited will be sent to the Trust's data office. All samples for patients that have opted out of having their records used for research purposes will be destroyed in line with local pathology policy. Once testing is completed the left-over samples will be disposed of as in line with the Human Tissue Act, 2004 and local Portsmouth Pathology protocols.

[name] lead researcher will correlate the results to the patients' identifiers in a password protected sheet. Results will then be clinically correlated to patient's records to deem patient outcomes and if they had an irAE. Data will be correlated into a password protected excel sheet kept on Trust computer system. Data will then be de-identified and patient identification will be removed. Identifiable patient data will be removed for data analysis the spread sheet would contain age in years, sex, cancer type, ICPI type, if they had an irAE, irAE type and when it occurred. This data will be in a password protected excel sheet. Statistics will be carried out via R.

Minimal patient data will be used in the write up of this study i.e., age in years, sex, cancer type, ICPI treatment type, and if they had an irAE. Information about irAE will include type of event, and when it occurred post treatment.

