7.0 SAMPLE SIZE

All adult oncology patients at Queen Alexandra Hospital who are prescribed FDA approved ICPI for the first time, providing they don't meet the exclusion criteria will be recruited. The sample size is expected to be around 120 patients, based on ICPI patient Portsmouth Hospital University Trust data from 2022. It is estimated that around 40-66% of patients on ICPI will have an irAE based on the literature.

Assuming an incidence rate of 40% for irAE, this study would require at least a sample size of 47 individuals assuming a significance criterion of $\alpha=0.05$ and power =80.

The study will run for 18 months and hopes to obtain at least a sample size of 47 individuals, depending on how many patients are referred for ICPI therapy. The study will end before 18 months if we recruit 150 patients before the end date.

The period of testing was decided upon discussion with the Oncology department, based on ICPI prescriptions provided by the pharmacy department.

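### The goal is an algorithm that flags patients likely to have an irAE, but the outcome under 3.1 is whether any blood test differs, with no performance measure, algorithm validation or multiplicity rule stated

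*Combined protocol and SAP*

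**What the plan says.** All references are to the combined protocol and SAP.

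- **Goal.** Section 3.1 asks whether an algorithm can be built to flag patients at higher risk of irAE, and whether malondialdehyde can be added to it. Sub-aim 4 in section 3.2 repeats this: "Can a blood test clinical algorithm be developed to stratify patients at high-risk of developing an irAE". Section 3.3 says: "This project could produce a clinical algorithm and/or blood test panel that successfully highlights patients at a high risk of developing irAE". Success is not defined.
- **Outcome under the primary objective.** The O line of section 3.1 reads: "Are any of the blood tests significantly different in those who develop irAE".
- **Other comparisons.** Sub-aim 1 asks: "Are there any established biochemistry, haematology and immunology blood tests that produce significantly different results". Sub-aim 3 asks: "Is malondialdehyde significantly raised in those who develop irAEs compared to those that do not".
- **Number of tests.** None is given. The lay summary (1.0) says the laboratory will "test them a month later for different routine blood tests as well as malondialdehyde". Section 3.2 names only IL-6 and malondialdehyde as study tests.
- **Criterion.** Section 7.0 states that "this study would require at least a sample size of 47 individuals assuming a significance criterion of" 0.05, with power 80 and a 40% irAE rate. About 120 patients are expected.
- **Analysis.** Section 4.1 says: "Statistics will be carried out via R". Section 6.3 likewise names only the software. The full validation in section 5.3 concerns the malondialdehyde method, not the algorithm.
- **Use of the results.** Section 13.0 intends them to lead to a panel that can be ordered for all patients on checkpoint inhibitors.

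**The concern.** The question asked and the outcome listed do not match. A significant difference in one test between patients with and without irAE does not show that a rule built from several tests identifies who will have one. As written, the study could meet its listed outcome with no working algorithm. It could also produce an algorithm with no agreed way of judging it.

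Two errors are then possible. An outcome met by any one of an uncounted set of tests becomes easier to meet by chance as the set grows. And an algorithm assessed in the patients used to build it looks predictive even when nothing predicts. Either result could carry an uninformative panel into routine requesting.

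**Working it through.** **Inputs from the documents.** Alpha 0.05, irAE rate 40%, minimum N 47 and expected N about 120 (all section 7.0). Events: 0.40 × 120 = 48 and 0.40 × 47 = 18.8, about 19. The number of tests m, the correlation between tests, the marker distribution and all effect sizes are assumptions, because the documents give none.

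**1. The plan's own figure.** The 47 cannot be derived from the stated inputs, because no effect size or test is given. It can be reached under several added assumptions, for example:
- One proportion, 40% against 60%, two-sided: n = [(1.96 + 0.8416) × √(0.4 × 0.6) / 0.2]² = 47.09.
- One marker compared between groups at a 40:60 split: d = (1.96 + 0.8416) / √(47 × 0.4 × 0.6) = 0.834.

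Every match found is for a single test at 0.05, none for a family of tests. This does not show that 47 is wrong.

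**2. Chance of meeting the any-test outcome when no test is related to irAE.** For independent tests the formula is 1 − 0.95^m. The last column is from simulated two-sample t-tests on normal markers.

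| m (assumed) | Independent | Correlation 0.5 (assumed) |
|---|---|---|
| 2 | 1 − 0.9025 = 9.8% | not computed |
| 5 | 1 − 0.7738 = 22.6% | about 18% |
| 10 | 1 − 0.5987 = 40.1% | about 28% |
| 20 | 1 − 0.3585 = 64.2% | about 42% |

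The two tests named in section 3.2 already give about 10%.

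**3. A difference is not prediction.** For one normal marker, AUC = Φ(d/√2). The difference detectable with 80% power at N=47 (d = 0.834) corresponds to an AUC of 0.72. At N=120, d = 2.8016 / √(120 × 0.24) = 0.522, an AUC of 0.64.

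**4. Algorithm judged in its own data, pure noise.** Simulated ridge logistic model keeping all markers, independent normal markers, 40% events, mean apparent AUC:

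| Markers | N=120 | N=47 |
|---|---|---|
| 5 | 0.61 | 0.68 |
| 10 | 0.67 | 0.76 |
| 20 | 0.74 | 0.88 |

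The true value is 0.50. Repeat runs agreed to within about 0.01.

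**5. Does internal validation correct this?** On the same noise, repeated 5-fold cross-validation averaged 0.495 to 0.503. Single null studies still exceeded 0.60 in 7–8% of cases at N=120 and 16–20% at N=47, so the estimate also needs a formal test. Permuting the irAE labels through the whole procedure rejected in 4.5–6.4% of null studies.

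**6. Test and interval can disagree.** A patient-bootstrap interval on the cross-validated AUC covered the truth in 98–99.8% of studies, so it is wider than its nominal 95%. With one informative marker (assumed AUC 0.70) among 5 to 20 at N=120, one run gave a lower limit above 0.50 in about 33–63% of studies, against permutation-test power of about 61–90%. Another run put that power at 56–84%. At N=47 it was 22–34%.

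**7. Keeping malondialdehyde separate.** One test at 0.05 plus a Holm-controlled family at 0.05 gives at most about 1 − 0.95 × 0.95 = 9.75% if independent. Simulation gave 7.5–10.2%.

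**The case against.** The strongest reply is that the plan is being held to things it does not say. Taking the parts in turn:

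- **Unadjusted testing.** A reader might infer that the sponsor has chosen to test without adjustment. The documents do not support that. Alpha appears once, as a sample-size input, and the plan is silent on adjustment. What stands is that no control is stated, so following the text as written provides none.
- **The only usable outcome.** A reader might also infer that the any-test comparison is the only outcome in the whole plan that can be applied. That is too strong. Sub-aim 3 is a separate, directional comparison of one named marker, and the any-test inflation does not apply to it. But it does not measure prediction either.
- **Assessment in the same patients.** The protocol does not say the algorithm will be judged in its own data. The apparent AUC figures are conditional on that.
- **Exploratory aims and modest use.** The aims ask whether an algorithm can be developed, and section 3.3 says only that one could result. Section 13.0 gives the panel's purpose as more consistent requesting and faster diagnosis, and no treatment decision based on the algorithm is described. This lowers the stakes. However, the protocol does not label the work exploratory, and it states no validation step between results and panel.
- **Reviewer assumptions.** The number of tests, correlation and marker model are indeed assumed, and the size is therefore a range. The missing count is itself part of the gap.
- **Missing flow chart.** It is not shown, but section 4.4 describes it as a summary of procedures. The objectives, sample-size and data sections are present.

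**Conclusion.** The point holds in this form. The primary goal is prediction, the outcome listed under 3.1 is a difference in any test, and the visible text gives no performance measure, algorithm validation, multiplicity adjustment or count of tests. This is more than missing detail, because the listed outcome can be met by chance and would not answer the question if met.

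The size depends on an unknown number of tests. For 5 to 20 tests the chance of a false positive is about 23–64% if independent and about 18–42% at correlation 0.5. If the algorithm were assessed in its own data, pure noise would give a mean AUC of about 0.61–0.74 at N=120 and 0.68–0.88 at N=47, assuming ridge logistic regression on independent normal markers. The qualitative conclusion needs none of these assumptions beyond more than one test being examined.

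**What to change.** Write the following into the plan before results are linked to patient records, which sections 5.4 and 9.0 place at May 2025.

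1. **Test list.** Fix and count the candidate tests.
2. **Primary outcome.** Replace the any-test outcome with the internally validated performance of the algorithm for irAE within 6 months of starting the checkpoint inhibitor. Report AUC, sensitivity and specificity at a prespecified risk threshold, and calibration. Use cross-validation or bootstrap with all selection and tuning repeated inside each resample. AUC alone is not enough, because flagging needs a threshold.
3. **One governing test.** Name a single test of AUC against 0.50, for example permuting the irAE labels through the whole procedure. Report the interval as a description of precision. If it is a patient bootstrap, keep all copies of a patient in the same fold, and say that it is conservative and may include 0.50 when the test rejects.
4. **Single-test comparisons.** Make them supporting, with Holm or Benjamini-Hochberg across the routine tests. Malondialdehyde may stay as one separate prespecified test. If Holm is used on the rest, state the overall error of about 8–10%.
5. **Panel.** Describe any resulting panel as awaiting validation in new patients.

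**Cost.** A test list, analysis wording and R code, with no extra samples or patients. Fewer tests will be declared significant. For example, the difference that 47 patients detect with 80% power in one test (d = 0.834) has about 50% power under Bonferroni across 10 tests, and about 95% at N=120. The reported AUC will be lower and its interval wide: half-width about 0.15–0.17 at N=120 and 0.28–0.29 at N=47 in the one-marker simulation. If recruitment ends near 47, power to show prediction will be low, and the plan should say so.
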